2. RESPONSIBLE PARTIES COUNTRY COORDINATING INVESTIGATORS

3. SUMMARY

A Low Intervention Study of the Effectiveness Of 13-Valent Pneumococcal Conjugate Vaccine (PCV13) Against Vaccine Type (VT) Pneumococcal Hospitalised Community Acquired Pneumonia (CAP) in Adults 60 Years and Older Using A Test Negative Design Study (TND) in A Well-Defined Area of the South of Madrid Region.

Version 3.0, dated 03 February 2022.

Main author: PPD , Pfizer S.L.U, Spain.

Rationale and background

The approval of the 13-valent pneumococcal conjugate vaccine (PCV13) for both adults and children offers the opportunity to prevent pneumococcal disease in the two groups of population with highest incidence rates, namely children <5 years of age and the elderly. In the Community of Madrid, PCV13 is recommended and reimbursed for all adults over

PFIZER CONFIDENTIAL CT45-GSOP-RF152.0 Low-Interventional Study Protocol Template 05-Dec-2019 Page 7 of 70 60 years of age not previously vaccinated with 23-valent pneumococcal polysaccharide vaccine (PPV23) nor PCV13 since January 2018. For this age group a single dose of PCV13 is recommended. In addition, it is recommended that individuals \geq 18 years with a chronic disease such as Chronic Obstructive Pulmonary Disease (COPD), diabetes, heart failure, regardless of previous vaccination status, will receive one dose of PCV13. Sequential immunisation with both vaccines (PCV13+PPV23) is recommended for high-risk immunocompromised patients \geq 18 years of age. This recommendation is supported by results of the CAPA study (Epidemiological study assessing the burden of hospitalised community-acquired pneumonia [CAP] due to *Streptococcus* pneumoniae (SP) in adults in Spain using urinary antigen detection [UAD] testing) that showed a significant proportion (9%) of hospitalised all-cause CAP cases were caused by PCV13 serotypes in adults 18 years and older.¹

The paediatric heptavalent pneumococcal conjugate vaccine (PCV7) was first available in Spain in June 2001 and incorporated in the Madrid regional immunisation programme (RIP) in 2006, remaining in the private market for other regions. From mid-2010 through 2016, Spanish regions introduced the 13-valent conjugate vaccine (PCV13) in their RIPs.

Adult vaccination with the 23-valent polysaccharide (PPV23) officially started in 2004, and with PCV13 in 2016 for some cohorts. Most adult pneumococcal vaccination occurs during annual influenza vaccination campaigns. Pneumococcal vaccination for adults in the Madrid region changed as of January 2018. An overview of pneumococcal adult vaccination is described in Table 1.

Note that for persons ≥ 60 years with past PPV23 administration, only those with underlying disease or at high risk will be given PCV13, and others without risk factors will not receive another pneumococcal vaccination (Table 1). Thus, in the ≥ 60 years age group, the population with PCV13 will be enriched for those with risk factors, and this will need to be accounted for in the analysis as a source of confounding (ie, confounding by indication).

Current PCV13 and PPV23 average uptake in Madrid Region as of March 2019 is described in Table 2, with a peak for PCV13 in people of 63 years old (see Table 2). People of over 60 years in the whole of Madrid region are 1,511,750 as of January 2018 (Instituto Nacional de Estadística, INE, www.ine.es).

The Regional Health System operates a database known as "Sistema de Información en Salud Pública y Alimentación" (SISPAL) [in English "Information System for Public Health and Food"] which includes information on previous vaccination history, including influenza, PPV23 and PCV13 vaccination, with lot number and date of administration per person.

Pneumococcal vaccination status will be based on whether receipt of ≥ 1 dose of PCV13 or PPV23 could be confirmed by electronic registries. All available vaccination data will be collected from the registry on subjects and time from vaccination will be incorporated in the analysis phase. Patients will be included regardless of the timing of their vaccination relative to their qualifying pneumonia admission but will be excluded from vaccine effectiveness

PFIZER CONFIDENTIAL CT45-GSOP-RF152.0 Low-Interventional Study Protocol Template 05-Dec-2019 Page 8 of 70

(VE) and serotype distribution analysis if they received pneumococcal vaccination \leq 30 days before hospitalisation for CAP because of risk of false positive UAD test. We will obtain previous influenza vaccination status (within the last year) via electronic registries as well.

Respiratory syncytial virus (RSV) has long been recognized as a problematic respiratory pathogen causing illness in children, but the scope and impact of RSV in adults is less well-defined. Severe disease occurs especially among those with compromised cardiac, pulmonary, or immune systems and in the elderly but estimates of the RSV disease burden requiring hospitalization in adults are limited. Previous studies have suggested that up to 10% of adults presenting with acute respiratory illness during the winter have RSV. Further, Pfizer is

Research question and objectives

Primary Objective

• To determine the effectiveness of PCV13 to prevent hospitalised VT-pneumococcal CAP among adults aged ≥60 years in Madrid using a TND, overall and among immunocompetent persons only.

Secondary Objective(s)

- To describe the distribution of SP serotypes using blood, high-quality respiratory cultures, and a serotype-specific UAD assay among adults 60 years of age and older with CAP.
- To determine the proportion of persons with respiratory pneumococcal carriage among adults 60 years of age and older presenting with CAP by testing saliva specimens using both conventional culture and the sensitive molecular method of polymerase chain reaction (PCR) for the detection of two target genes (lytA and ply).
- To describe the proportion of participants with CAP and with *S. pneumoniae* (SP+CAP) who present with underlying at-risk and high-risk medical conditions.
- To describe the frequency and type of antibiotic resistance among SP isolates, overall and by specimen type.

Exploratory Objectives

- To estimate incidence rates for hospitalised CAP and SP+CAP (both overall and radiologically confirmed) in the surveillance region within the limitations of the expected under ascertainment of hospital-based screening process and current diagnostic testing.
- To compare the effectiveness of PPV23 to that of PCV13 in preventing cases of hospitalised VT-pneumococcal CAP among adults aged ≥60 years using a test-negative study design, overall and among immunocompetent persons only.
- To compare pneumococcal serotype results from high-quality respiratory specimens (standard –of care), UAD1/2 (study procedure), and saliva specimens taken for carriage testing (study procedure).
- To estimate incidence rates for hospitalised CAP among adults aged ≥60 years with underlying at-risk and high-risk medical conditions, in aggregate and for individual risk conditions within the limitations of the expected under ascertainment of hospital-based screening process and current diagnostic testing.

Additional 2019 Novel Coronavirus Disease 2019 (COVID-19)-related Exploratory Objectives

- To determine if the frequency of pneumococcal infection differs between hospitalised CAP patients with COVID-19 infection compared to those without COVID-19 infection, overall and stratified by age, sex, and pneumococcal risk status.
- Among the subset of hospitalised CAP patients with COVID-19 identified, to determine if the proportion who experience severe clinical outcomes (eg, intensive care unit [ICU] stay, mechanical ventilation, prolonged hospitalisation, and sequelae) differs between those with pneumococcal co-infection compared to those without pneumococcal co-infection, overall and stratified by age, sex, and pneumococcal risk status.
- Using a test-negative design to determine the VE of PCV13 against severe COVID-19 clinical outcomes among COVID-19 positive hospitalised CAP patients, overall and among immunocompetent persons only.
- To assess if pneumococcal carriage differs for those with current or past COVID-19 infection, overall and stratified by age, sex, and pneumococcal risk status.

Additional 2022 Respiratory Syncytial Virus (RSV) Exploratory Objective

• To determine the proportion of persons with RSV infection among adults 60 years of age and older presenting with CAP by testing saliva specimens using the PCR method.

Study design

This study is a low interventional, prospective, multicentre, hospital-based study involving adults 60 years of age and older hospitalised with CAP at participating sites. Hospital surveillance data will be used for incidence rates calculations. Vaccine effectiveness will be calculated using a TND. The approximate study duration will be 4 years.

Population

This study will prospectively enroll adults, aged 60 years and over, who are hospitalised with CAP in one of the study hospitals: Hospital Universitario de Móstoles, Hospital Universitario Fundación de Alcorcón, and Hospital Rey Juan Carlos de Móstoles (as of February 2022, additional sites may be included at a later date).

Variables

Please see Section 10 for full listing. In summary, the screening step will collect demographic information, eligibility for the study, whether consented, any standard of care

PFIZER CONFIDENTIAL CT45-GSOP-RF152.0 Low-Interventional Study Protocol Template 05-Dec-2019 Page 11 of 70

(SOC) test results. If consent is given, then further data collection and enrolment would include: medical and vaccination history, smoking and alcohol use, details of current illness including all symptoms, treatment, severity score, vital signs and test results. At follow up, confirmation of CAP or alternative diagnosis, event disposition and vital status would be recorded at two visits: 30 and 180 days after hospital admission.

Data sources

Data will be collected from the hospital, including radiology and laboratory results, as well as primary care medical records.

Study size

The required sample size depends on the accrual of immunocompetent VT-CAP cases, the VE point estimate, percentage of individuals vaccinated, as well as other factors. Based on current estimates, the overall number of subjects to be enrolled is expected to be between 2,000 and 5,500 and required time for enrolment will be between 1.7 and 4 years, depending on the values for the parameters mentioned above and enrolment rates. See Section 12.1.2 for full information on these calculations. As the required number of enrolled subjects is highly dependent on the proportion of CAP subjects that have VT pneumococcal CAP and the proportion of the population vaccinated, the required sample size may be adjusted based on ongoing information from UAD testing results and vaccine exposure data if needed. An interim analysis will be conducted after accrual of 170 VT-cases but, given additional subjects may be needed to allow for adequate statistical power, at least 4 years of enrolment is planned.

Data analysis

Vaccine Effectiveness will be calculated as follows. Odds of having received PCV13 for cases and controls will be constructed and compared using odds ratios (OR) and 95% Confidence interval (CIs). We will calculate VE as 1-OR x 100. In addition to constructing crude OR and VE estimates, we will also perform propensity score matching cases and controls using potentially confounding factors for VE, and then construct a conditional logistic regression to assess PCV13 and PPV23 VE. For the other study objectives, descriptive analysis will be carried out, presenting the absolute and relative frequencies of the qualitative variables and the main measures of centralization and dispersion in case of quantitative variables. CAP incidence rates per 100,000 inhabitants of the study age group will be assessed based on CAP events captured on screening log during the recruitment period in the participating sites. Methodologies for the statistical analyses of the data collected in this study are outlined here and will be provided in detailed in the full study protocol and statistical analysis plan (SAP).

Milestones

Milestone	Planned date
Completion of feasibility assessment	Q2 2020
Start of data collection, First Subject First Visit (FSFV)	March 2021
End of data collection, Last Subject Last Visit (LSLV)	Q1 2025
Interim analysis	After approximately 170 immunocompetent VT- CAP cases available for analysis [~Q2 2022]
Study results	Q2 2025
Final study report	Q3 2025

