12.1.3. Analysis Populations

12.1.3.1. Vaccine Effectiveness CAP Population (Primary Analysis Population)

The Primary Analysis Population will include all participants who:

- 1. Meet all inclusion and exclusion criteria.
- 2. Have a final diagnosis consistent with CAP (CAP-Radiologically Confirmed; CAP-Not Radiologically Confirmed or CAP-no chest radiology done).
- 3. Meet the definition of either case or test-negative control from Section 12.1.1.
- 4. Have \geq 5 combined years of pneumococcal vaccination history available.
- 5. Did not receive any pneumococcal vaccination ≤30 days prior to urine sample collection.
- 6. Have not received PCV20 if available in surveillance region during study.

This population will be analysed overall and restricted to immunocompetent subjects which will be all subjects not noted to the immunocompromised in Table 7.

Table 7.Categorization of Risk Factors by Immunocompetence³

Risk factor	Spain's Categorization		
Age	60 +		
Diabetes mellitus	immunocompetent		
Alcoholism	immunocompetent		
Chronic heart disease	immunocompetent		
Chronic liver disease	immunocompetent		
Chronic lung disease	immunocompetent		
Smoking	immunocompetent		
Congenital or acquired asplenia	immunocompromised		
Cerebrospinal fluid leak	immunocompetent		
Cochlear implant	immunocompetent		
Congenital or acquired immunodeficiencies	immunocompromised		
HIV infection	immunocompromised		
Chronic renal failure	immunocompromised		
Nephrotic syndrome	immunocompromised		
Leukemia	immunocompromised		
Hodgkin's disease	immunocompromised		
Lymphoma	immunocompromised		
Generalize malignancy	immunocompromised		
Iatrogenic immunosuppression	immunocompromised		
Solid organ transplant	immunocompromised		
Multiple myeloma	immunocompromised		
Antineoplastic chemotherapy	not specified		
Occupational risk with exposure to metal fumes	not specified		
Bone marrow transplantation	immunocompromised		
Neurologic diseases (eg, cerebral palsy and seizures)	not specified		
Prior IPD	immunocompetent		

These populations will serve as the primary analysis population for the primary endpoint and the secondary objective of calculating VE for PPV23.

³ Official Regional Immunisation Programme in the Community of Madrid, 2019.

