12.4.2. CAP Incidence Rate

Incidence rates (IR) per 100,000 inhabitants of the study age group will be calculated with their respective 95% confidence intervals.

Numerator: The numerator will include all CAP events – both involving study subjects and other unconsented patients captured on screening log as residents of the hospitals' geographical catchment area. Frequent retrospective review of admissions assigned pneumonia ICD discharge codes will be undertaken monthly to ensure no CAP events are missed from the screening log. Efforts will also be made to assess how many persons from the district were hospitalised for pneumonia outside of the surveillance region.

For SP+CAP, the proportion of CAP events among study subjects with pneumococcus identified by any means, will be multiplied by the calculated CAP incidence rate. For radiologically confirmed CAP, the proportion of CAP events among study subjects that is radiologically confirmed will be multiplied by the calculated CAP incidence rate. Other more complex adjustment processes will also be explored if there is adequate detail captured in the screening log, such as calculation the proportion with pneumococal infection within specific risk/age strata or multiple imputation.

Denominator: Annual population data over 60 years old and estimated person-years data for this age group will be obtained from INE (National Statistical Institute). To determine denominators (catchment area), calculations will be made based on the following parameters: age-specific strata of the total population in the region of Madrid; age-specific strata of total hospital discharges in the region of Madrid; age-specific strata of hospital discharges of the Móstoles (2 hospitals) and Alcorcón (1 hospital). Catchment area is calculated as the proportion of the Móstoles and Alcorcón hospital discharges compared to total hospital discharges in the region of Madrid. These percentages are then applied to the total population of the region of Madrid and hence, catchment population in the Móstoles and Alcorcón hospitals by age group are estimated. If population denominators for adults aged ≥ 60 years are available for underlying at-risk and high-risk medical conditions, incidence will be calculated specifically for these risk groups in aggregate and for individual risk conditions that are of sufficient size as outlined in the SAP.

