#### 2. INTRODUCTION

This statistical analysis plan (SAP) provides the detailed methodology for summary and statistical analyses of the data collected in Study B1851202. This document may modify the plans outlined in the protocol; however, any major modifications of the primary endpoint definition or its analysis will also be reflected in a protocol amendment. Note that any text taken directly from the protocol is *italicized*, with exceptions note where it appears.

This study is designed to evaluate the effectiveness of 13-valent pneumococcal conjugate vaccine (PCV13) in preventing hospitalised vaccine-type (VT) community acquired pneumococcal (CAP) disease among adults aged ≥60 years in Madrid using a prospective study to collect data for test-negative design (TND) analysis, overall and among immunocompetent persons only. Further this study will also measure the proportion of CAP that is associated with Respiratory Syncitial Virus (RSV) infection.

Pneumococcal vaccination status will be based on whether receipt of ≥1 dose of PCV13 or PPV23 could be confirmed by electronic registries. All available vaccination data will be collected from the registry on subjects and time from vaccination will be incorporated in the analysis phase. Patients will be included regardless of the timing of their vaccination relative to their qualifying pneumonia admission but will be excluded from vaccine effectiveness (VE) and serotype distribution analysis if they received pneumococcal vaccination ≤30 days before hospitalisation for CAP because of risk of false positive urinary antigen detection (UAD) test.

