#### 4.7. Serotype Distribution CAP Population

This population will include the per-protocol population and those who:

have a final diagnosis consistent with CAP (CAP-radiologically confirmed; CAP not

radiologically confirmed or CAP-no chest radiology done).

- did not receive any pneumococcal vaccination ≤30 days prior to urine sample collection,
   and
- pneumococcal serotype identified from UAD1/2 test results, Binax, blood culture or highquality respiratory culture (e.g., from bacterial isolate).

Events with the same serotype result involving rehospitalization  $\leq$ 30 days from the date of discharge of the earlier hospitalization will be considered same event in the analysis.

DMB02-GSOP-RF02 5.0 Statistical Analysis Plan Template 05-Dec-2019
PFIZER CONFIDENTIAL
Page 25
TMF Doc ID: 98.03

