## 4.8.5. Sp+ Subpopulation

This subpopulation is composed of the per-protocol population that are also Sp+ by any of the following three diagnostic methods:

- microbiology culture results of S. pneumoniae as a pathogen from local lab entered in the eCRF; or
- 'POS' results from Binax assay; or
- 'POS' results from UAD assay for any of the 24 serotypes.

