#### 6.3.6.1. COVID-19 Related Endpoint 2 - Main Analysis

The patients with COVID-19 will be divided into two groups:

- those with coinfection with Sp identified by any means (e.g., UAD, Binax, bacterial culture)
- Those without coinfection with Sp identified by any means (e.g., UAD, Binax, bacterial culture)

The severe clinical outcomes are:

- Admitted to ICU (yes vs. no)
- PaO2/FiO2 ratio <250 mmHg (yes vs. no)

DMB02-GSOP-RF02 5.0 Statistical Analysis Plan Template 05-Dec-2019
PFIZER CONFIDENTIAL
Page 39
TMF Doc ID: 98.03

- Respiratory rate >30 breaths/min (yes vs. no)
- Died (yes vs. no)
- Received mechanical ventilation (yes vs. no)
- Diagnosed as ARDS (yes vs. no)
- Any one of the above (yes. vs. no)

The difference in the severe clinical outcomes between the two groups will be evaluated using Chi-square or Fisher's Exact test, as appropriate.

The analysis will also be done stratifying by age group (60-74 years,75-84 years and ≥85 years), sex, and pneumococcal risk status.

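### The 30-day post-vaccination exclusion, made because of false-positive UAD results, is not carried into several other analyses that rely on a positive UAD

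*Protocol*

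**What the plan says.** Protocol Section 3 (Rationale and background) states: "Patients will be included regardless of the timing of their vaccination relative to their qualifying pneumonia admission". It then removes from vaccine effectiveness (VE) and serotype distribution those vaccinated against pneumococcus at most 30 "days before hospitalisation for CAP because of risk of false positive UAD test". SAP Section 2 repeats that scope: VE "and serotype distribution analysis if they received pneumococcal vaccination ≤30 days before hospitalisation for CAP".

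The criterion is written into three analysis sets:
- the VE population in Protocol 12.1.3.1: "Did not receive any pneumococcal vaccination ≤30 days prior to urine sample collection";
- the serotype distribution population in Protocol 12.1.3.4;
- the corresponding SAP population in 4.7: "did not receive any pneumococcal vaccination ≤30 days prior to urine sample collection".

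Elsewhere a positive UAD counts without regard to vaccination date. In SAP 4.8.5 one of three sufficient routes into the Sp+ set is "POS' results from UAD assay for any of the 24 serotypes". For SP+CAP incidence, Protocol 12.4.2 says that "the proportion of CAP events among study subjects with pneumococcus identified by any means, will be multiplied by the calculated CAP incidence rate". COVID-19 Endpoint 2 in SAP 6.3.6.1 defines its exposed group as "those with coinfection with Sp identified by any means (e.g., UAD, Binax, bacterial culture".

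**The concern.** The stated reason for the exclusion is a property of the test result: a recent dose can turn the UAD positive without infection. A result judged unreliable for VE does not become reliable when it feeds another endpoint, and neither document explains the narrower scope. Eligibility does not remove these patients, since they are enrolled by design.

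At stake are one descriptive secondary endpoint (risk conditions among Sp+), several exploratory endpoints, and the consistency of the report, which would apply the rule to some UAD-based results and not to others. The error need not be neutral. Protocol Section 3 says that people aged 60 or over with PCV13 will be enriched for risk factors, and the risk-condition endpoint estimates how common those factors are among Sp+ patients.

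**Working it through.** **Step 1: where the rule is and is not.** The documents give no figure to reproduce here, so the check compares definitions.

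| Set or analysis | Uses UAD? | 30-day rule? |
|---|---|---|
| VE population (Protocol 12.1.3.1) | Yes | Yes |
| Serotype distribution population (Protocol 12.1.3.4, SAP 4.7) | Yes | Yes |
| Per-protocol and CAP populations (SAP 4.3, 4.5) | Parent sets | No |
| UAD and Sp+ subpopulations (SAP 4.8.1, 4.8.5) | Yes | No |
| Secondary endpoint 3, risk conditions among Sp+ (SAP 6.2.3.1) | Yes, through Sp+ | No |
| SP+CAP incidence (Protocol 12.4.2) | Yes | No |
| COVID-19 Endpoints 1 and 2 (SAP 6.3.5.1, 6.3.6.1) | Yes | No |
| UAD versus culture, UAD versus saliva (SAP 6.3.3.1) | Yes | No |
| Culture versus saliva; COVID-19 Endpoints 3 and 4 | No | Not needed |

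Two further points:
- SAP 6.2.1.1 runs the serotype distribution on the whole tested CAP population and on Sp+, and does not name the 4.7 set that carries the rule.
- The window is counted from hospitalisation in Protocol Section 3 and SAP Section 2, but from urine collection in Protocol 12.1.3.1, 12.1.3.4 and SAP 4.7. A patient vaccinated 29 days before admission whose urine is taken 2 days after it (day 31) is excluded under one and kept under the other.

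**Step 2: size.** Let f be the share of CAP patients vaccinated in the prior 30 days and q the chance that such a patient has a vaccine-induced positive UAD. The documents give neither. Protocol 12.1.2 gives a 9% vaccine-type share and 1,800 CAP admissions a year.

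False positives per 1,800 = 1,800 × f × q × (1 − 0.09). Observed share = 0.09 + f × q × 0.91.

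An anchor for f: Protocol Section 7 gives about 8% PCV13 uptake by September 2019. Spread evenly over the 21 months from January 2018 (21 × 30.4 / 30 = 21.3 thirty-day periods), this is 8 / 21.3 = 0.38%, taken as 0.4%. The age-specific Table 2, weighted by cohort size, gives 13.8% at ages 60-75, hence 13.8 / 21.3 = 0.65%.

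| f (assumed) | q (assumed) | 9% share reads as | False positives per 1,800 |
|---|---|---|---|
| 0.2% | 0.2 | 9.04% | 0.7 |
| 0.4% | 0.5 | 9.18% | 3.3 |
| 1% | 1.0 | 9.91% | 16.4 |
| 2% | 1.0 | 10.82% | 32.8 |

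**Step 3: effect on the high-risk share.** Protocol 12.1.2 expects 36% of CAP admissions to be immunocompromised. Apply that to the 9% and let every false positive be immunocompromised, the worst case.
- Central inputs: (0.36 × 9 + 0.18) / 9.18 = 3.42 / 9.18 = 37.3%.
- Top of both ranges: (3.24 + 1.82) / 10.82 = 46.8%.

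For comparison, 9% of the base-case 3,063 enrolled is about 276 positives, and the 95% half-width around 36% is 1.96 × √(0.36 × 0.64 / 276) = 5.7 points. The full Sp+ set also contains non-vaccine types and Binax positives, so the base is larger and the shift smaller than shown.

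**Step 4: which remedy.** One option is to void the UAD result and keep the patient. SAP 3.4 makes anyone not positive by any method Sp-, unless all three methods are missing. A recent vaccinee with true pneumococcal CAP detectable only by UAD would then be counted as negative and stay in the denominator. Excluding the patient avoids that opposite error.

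**The case against.** The strongest reply is that this is too small to matter. On central inputs the high-risk share moves by at most 1.3 points, against a sampling half-width of 5.7. The incidence estimates are already declared conservative, the COVID-19 analyses are conditional on enough cases, and the primary endpoint is protected. The inputs are also weak: some cohorts received PCV13 from 2016, which lowers f, while PPV23 doses and concentration in influenza campaigns raise it at times, and general-population uptake may not match that of CAP inpatients. All of this stands, and it limits the point to one of consistency.

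It can also be said that Protocol 12.1.3.4 is headed as the secondary analysis population and so might cover secondary endpoint 3. SAP 6.2.3.1 does not follow that reading; it uses the CAP and Sp+ sets.

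Stronger readings that a reader might infer are not supported:
- **A PCV20 roll-out would produce many false positives.** Protocol 9.1 expects initial PCV20 use mainly among people ageing into the over-60 group, not a mass campaign. In Table 4, 16,723 of 22,487 pneumonia admissions (74%) are over 74.
- **The COVID-19 comparisons are biased in a known direction.** Most doses are given in influenza campaigns, but nothing in the documents shows how that season relates to COVID-19 status among these patients.
- **The agreement analysis counts false infections.** It classifies nobody as infected; a vaccine-derived UAD positive appears there as discordance.
- **The VE analysis is exposed.** SAP 6.1.1.1 does not restate the rule in its exclusion list, but Protocol 12.1.3.1 and SAP Section 2 both apply it to VE.

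**Conclusion.** The gap is real on the text: the plan accepts that a UAD within 30 days of vaccination may be falsely positive, yet applies the consequence only to VE and serotype distribution. It remains open for secondary endpoint 3 among Sp+, SP+CAP incidence, COVID-19 Endpoints 1 and 2, and the two UAD agreement comparisons.

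The effect is probably small, about 3 per 1,800 CAP patients at f = 0.4% and q = 50%, with about 1 to 33 over the wider ranges; all of these rest on assumed inputs. For the at-risk and high-risk shares among Sp+ the likely direction is upward. This assumes that recently vaccinated CAP patients carry more risk conditions than other Sp+ patients, which the stated enrichment of PCV13 recipients makes plausible but does not prove. No direction is established for the COVID-19 endpoints.

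**What to change.** Extend the existing patient-level exclusion (any pneumococcal vaccination within 30 days before collection of the urine sample) to numerator and denominator of:
- secondary endpoint 3 among Sp+ (SAP 6.2.3.1); the shares among all CAP do not use UAD and need no change;
- the Sp+ proportion that multiplies the CAP incidence rate (Protocol 12.4.2); the CAP incidence itself is unchanged;
- COVID-19 Endpoints 1 and 2 (SAP 6.3.5.1, 6.3.6.1);
- the UAD-versus-culture and UAD-versus-saliva comparisons (SAP 6.3.3.1).

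Do not reclassify these patients as Sp- on the remaining methods.

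Apply the SAP 4.7 set in 6.2.1.1. Its last criterion should then read as in Protocol 12.1.3.4, a valid result and not an identified serotype, or the tested denominator would be lost. Use urine collection as the single anchor date in both documents.

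The cost is roughly 0.4-1% of participants (assumed) in these analyses, and edits to several SAP sections and to the wording of Protocol 12.4.2. Vaccination dates are already collected from the registry. Multiplying by a proportion from which recent vaccinees are excluded assumes that their true Sp+ share is like that of the other patients, a minor assumption at this size.
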